The study protocol was pre-registered at ClinicalTrials.gov NCT04573972 <https://clinicaltrials.gov/ct2/show/NCT04573972> prior to any data collection. Clinical Trials pre-registrations do not include analysis plans. Consequently, this OSF pre-registration, including an analysis plan, was filed prior to downloading any data from W2H.

Participant flow diagram: ([name] or [name], please fill in numbers)

XXX people entered W2H portal	→ XX did not consent
↓ XX consented	→ XX did not fully enroll
↓ XX fully enrolled	→ XX not linked to a fully-enrolled partner
↓ XX has fully-enrolled partner	→ XX did not provide synced FitBit & Aware data for at least 1 out of 7 days of pre-intervention period or has partner who did not provide synced data for 1 out of 7 pre-intervention days
↓ XX provides baseline data	→ XX requested to be unenrolled prior to randomization
↓ XX included in study and randomized to condition (N= XX/2 pairs)	
↓ XX in the regular incentive condition & YY in the social incentive condition	

Data collection procedures

Study participants were recruited at Carnegie Mellon University through posting on the subject pool website and announcements to undergraduate classes. Potential participants had to sign up with a friend, with at least one member of the friend pair being a current CMU student. Participants had to own an IOS or Android smartphone and be willing to download the FITBit and Aware apps to track their activity and location for 5 weeks.

Stopping rule

Our stopping rule was to close enrollment once 220 people were fully enrolled or when Oct 15, 2020 occurs, whichever comes first. We opened enrollment on Oct 1, 2020 and closed it on Oct 11, 2020 because at that point 220 people had fully enrolled. Fully enrolling includes consenting, completing the intake survey, providing a code for a partner who was also enrolling, and downloading the FitBit and Aware apps. Some of the individuals who fully enrolled were not included in the study because their partner did not fully enroll.

Manipulated variables

There was one manipulated variable (treatment condition) with two levels: regular vs. social incentive.

Measured variables

Primary dependent variables (as pre-registered on Clinical Trials)

1. The mean daily treatment period step count (averaged across all of a participant's included treatment period days) minus the mean daily baseline period step count (averaged across all of a participant's included baseline period days).

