2. The mean daily followup period step count (averaged across all of a participant's included followup period days) minus the mean daily baseline period step count (averaged across all of a participant's included baseline period days).
3. Number of days during treatment period when participant reached goal. Converted to a fraction by dividing by the number of included treatment period days.
4. Number of days during followup period when participant reached goal. Converted to a fraction by dividing by the number of included followup period days.
5. Change in score on UCLA Loneliness Scale. Score on post-test (range 0 to 60) minus score on pretest.

Secondary dependent variables (as pre-registered on Clinical Trials)

6. Number of days participant walked together with partner during treatment period, as assessed via self-report on daily survey

7. Number of days participant walked together with partner during followup period, as assessed via self-report on daily survey
8. Number of days participant walked together with partner during treatment period, as assessed via Aware data
9. Number of days participant walked together with partner during followup period, as assessed via Aware data

Indices

The UCLA Loneliness Scale is measured on both the intake and exit surveys. It consists of 20 items, each scored as 0, 1, 2, or 3. The scores from all 20 items are added to form a total score ranging from 0 to 60.

Inclusion Criteria

In order to be included in the study, each participant must fulfill all of the following

- Consent
- Fully enroll, including authorizing FitBit app and installing Aware app
- Link to a friend who fully enrolls in the study before the registration deadline
- Participants who request to unenroll are excluded.
- Provide synced step data for at least one day of the 7-day baseline period
 - That is, there must be at least one baseline day with a non-zero step count
- Provide Aware data for at least one day of the 7-day baseline period

Exclusion of individual data points

- Days that a participant has a value of 0 for steps walked will be considered missing data (assume there was no sync for that day)
- For each participant, we will compute the mean and standard deviation of number of daily steps, computed over all days of the study with non-zero step counts. Days with a step count that are > 3 standard deviations away from the participant's own mean will be excluded from analyses (treated as missing data).

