- Average step count will then be computed for each phase, after treating these excluded data points as missing.

Data File Structure

- Note: remove the research team participants from the datafile.
- Daily file (35 rows per participant -- one row per day of the protocol)
 - Subject id
 - Dyad id (links together the two subject ids in a friend pair)

- Phase (baseline, incentive, followup)
- Day of protocol (1 - 35)
- Calendar date
- FitBit steps walked
- Met goal (yes or no; missing for baseline period)
- Synced FitBit data (yes or no)
- Synced Aware data (yes or no)
- Correct end-of-day survey sent (yes or no; missing for baseline period)
- Answered end-of-day survey (yes or no; missing for baseline period)
- Walked with partner (yes or no; missing if wrong survey sent or survey not answered)
- Walked at least 2,000 steps with partner (yes, no, or missing)
- Walked in-person or virtually with partner
- Study file (1 row per participant)
 - Subject id
 - Included in study (for ITT analysis)
 - Included in main analysis
 - Dyad id (links together the two subject ids in a friend pair)
 - Date started baseline period
 - Date started incentive period
 - Goal number of steps
 - Total amount earned during study
 - All responses from baseline survey
 - All responses from exit survey

ITT analysis

- Includes all Ss who meet the inclusion criteria, even if they have a lot of missing data.
- Similar to the main analysis described below, but it doesn't exclude Ss based on missing data.
- It does still exclude individual data points, same as in the Main Analysis

Main Analysis

In order to be included in the main analyses, each participant must also fulfill all of the following

- Provide synced step data for at least 2 days of the 7-day baseline period
- Provide synced step data for at least 4 days of the 14-day treatment period
- Provide synced step data for at least 4 days of the 14-day followup period
- Be paired with a partner who is also included in the main analyses

Secondary Analyses

- Secondary analyses will explore the relationships among change in UCLA Loneliness score (intake to exit survey), change in mean daily steps walked from baseline to post-incentive period, and percentage of days during post-incentive period when the dyad walked together. Specifically, we will test whether the effect of study condition on change in steps walked is mediated by change in loneliness score and percentage of days when the dyad walked together.

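### The inclusion list that defines ITT and the participant flow diagram apply different rules, so the ITT set as written need not match the set that was randomised

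*SAP*

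**What the plan says.** **Inclusion list** (Inclusion Criteria, same list in protocol and SAP). The participant must meet "Provide synced step data for at least one day of the 7-day baseline period" and "Provide Aware data for at least one day of the 7-day baseline period". The partner condition is "Link to a friend who fully enrolls in the study before the registration deadline". A further bullet excludes anyone who asks to unenrol, with no time limit.

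**Full enrolment** (Stopping rule, both documents). "Fully enrolling includes consenting, completing the intake survey, providing a code for a partner who was also enrolling, and downloading the FitBit and Aware apps". Baseline data are not part of it.

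**ITT** (SAP, ITT analysis). "Includes all Ss who meet the inclusion criteria, even if they have a lot of missing data". Randomisation is not mentioned.

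**Flow diagram** (SAP, Explanation of existing data). Before randomisation it removes people without baseline data of their own, and also anyone who "has partner who did not provide synced data for 1 out of 7 pre-intervention days". It then removes those who asked to unenrol before randomisation. The next box is "XX included in study and randomized to condition (N= XX/2 pairs". All counts are unfilled.

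**Main analysis set** (SAP, Main Analysis). This adds minimum numbers of days with step data and requires that the partner also qualify for the main analyses. ITT has no equivalent condition.

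**The concern.** Assignment to condition was by dyad, so an ITT set should be the assigned dyads. The inclusion list does not deliver that. A participant with seven good baseline days whose partner has none is in ITT by the list but out before randomisation by the flow diagram. A participant who was randomised and later asked to unenrol is in the randomised box of the diagram but out of ITT by the list. The first mismatch adds people to ITT who should have no condition. The second removes people after assignment, which is the loss an ITT set is meant to prevent.

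What is at stake is the denominator and composition of the ITT analysis for each of the five primary outcomes, and whether the reported flow diagram and ITT tables will agree.

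**Working it through.** The plan states no figure to reproduce, so the check is mainly a comparison of rules.

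**Step 1. Baseline data.** Take linked, fully enrolled pairs in which nobody unenrols, and apply both rules to one member.

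| Own baseline data | Partner's baseline data | Inclusion list, hence ITT | Flow diagram, randomised |
|---|---|---|---|
| yes | yes | in | in |
| yes | no | **in** | **out** |
| no | yes | out | out |
| no | no | out | out |

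The rules disagree in one combination of four.

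**Step 2. Unenrolment.** Take pairs in which both members gave baseline data.

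| Person | Inclusion list, hence ITT | Flow diagram, randomised |
|---|---|---|
| asked to unenrol before randomisation | out | out |
| asked to unenrol after randomisation | **out** | **in** |
| partner of someone who unenrolled before randomisation | in, read literally | not stated, though the next box counts pairs |

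The rules disagree in the second row. In the third, the diagram is silent.

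**Step 3. Illustrative size of the Step 1 gap.** Inputs: N = 220 fully enrolled (Stopping rule), and q, an assumed probability that a person gives no qualifying baseline data, independent between partners. The documents give no value for q.

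- ITT by the list: N(1 − q)
- Randomised by the diagram: N(1 − q)²
- Gap: N(1 − q) − N(1 − q)² = Nq(1 − q)

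| q | ITT by list | By diagram | Gap (people) |
|---|---|---|---|
| 1% | 217.8 | 215.6 | 2.2 |
| 2% | 215.6 | 211.3 | 4.3 |
| 5% | 209.0 | 198.5 | about 10 |
| 10% | 198.0 | 178.2 | 19.8 |

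Counted by dyad instead: 220 / 2 = 110 dyads at most. If 2% to 10% have exactly one member without baseline data, that is 110 × 0.02 = 2.2 to 110 × 0.10 = 11 people.

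The 220 is a ceiling: the Stopping rule says some of these people were left out because their partner did not fully enrol. If friends tend to fail together, the gap is smaller for the same q.

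**Step 4. Would the extra people change the estimate?** The SAP model has condition as its independent variable. A person removed before randomisation has no value for it and cannot enter the regression, so the treatment contrast does not move. Only if such people had been given a condition would it move. Their share of ITT would then be Nq(1 − q) / N(1 − q) = q. If the social incentive did nothing for them, the contrast would shrink by about that share.

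**The case against.** The strongest reply is that the intended set can be inferred. The SAP's study file has a flag for inclusion in the study, marked as the one for ITT, and the flow diagram's randomised box also speaks of inclusion in the study. Together they suggest that ITT was meant to be the randomised pairs and that the inclusion list is an incomplete restatement. This is a fair reading of intent, but the ITT section refers to the inclusion criteria, and nothing reconciles the two.

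Three stronger readings are tempting, and the documents do not support them.

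- *Unpaired people dilute the social-incentive effect.* This needs them to hold a condition. It is conceivable: W2H randomised individuals at the end of baseline and staff then aligned pairs by hand, while the model's covariates allow for partners who enrolled on different days. But the flow diagram places the partner exclusion before randomisation, and no case of an unpaired person being assigned is shown.
- *The analyst can choose the ITT sample after seeing data.* Who holds a condition was settled when the trial was run, and an analyst cannot later give a condition to someone who has none. The room that remains concerns the reported denominator and people who unenrolled after assignment.
- *A lone member was randomised after the partner withdrew.* The diagram does not say what happened to that partner. Silence in an unfilled template is not evidence that the partner was kept.

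It is also true that the main analysis has its own partner rule, so unpaired people cannot enter it.

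**Conclusion.** The inconsistency is real. The inclusion list and the flow diagram differ on the partner's baseline data and on when unenrolment counts, and ITT is tied to the list. The set labelled ITT need not equal the set that was randomised.

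The consequence is limited to the ITT analyses of the five primary outcomes. For the partner rule, the probable effect is an unclear denominator rather than a biased contrast. The illustrative 2 to 20 people rests on an assumed 1% to 10% of individuals without baseline data, independence between partners, and the ceiling of 220. The documents do not show that even one such person exists. For unenrolment, the list read literally removes assigned people from ITT; the documents give no basis for a number. The point merits correction because the remedy is cheap and a set called ITT should follow assignment.

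**What to change.** 1. In the SAP, define ITT as every member of every dyad assigned a condition, analysed by that condition. Include those who asked to unenrol after assignment, where their data may be used.
2. In the inclusion list of both documents, add the flow diagram's requirement on the partner's baseline data, and limit the unenrolment exclusion to requests made before assignment.
3. In the flow diagram, state what happened to the partner of anyone who unenrolled before randomisation. Report the number of pairs directly, not as half the number of people.
4. State whether any unpaired person received a condition from W2H. If so, report how many and how they were handled.

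With the first two changes, the gaps shown in Steps 1 and 2 of the working close. Enrolment and assignment were already complete, so the eligibility wording should record what was done.

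The cost is wording and a small change in the ITT sample. It may lose a few unpaired participants relative to the current list and regain some who unenrolled after assignment. The latter would bring missing data, handled by the existing rules: a step change of zero when a whole phase is missing, and the intake value in place of a missing exit survey. Those rules do not say what value the goal-days fraction takes when a phase has no included days. That question already arises under the current ITT definition and needs one added sentence.

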Analysis Plan

Study Title: Using Social Connectedness to Increase Physical Activity

Identifier: NCT04573972

Unique Protocol ID: STUDY2019_00000296

Date: October 22, 2021

Hypotheses

Hypotheses are pre-registered at ClinicalTrials.gov NCT04573972

<https://clinicaltrials.gov/ct2/show/NCT04573972>

We hypothesize that, compared to the regular incentive condition, participants in the social incentive condition will show a larger positive change in daily steps walked during the baseline period to daily steps walked in the post-intervention period.

Study Design

Participants volunteered for the study with a friend; thus randomization occurs at the level of the dyad, with half the dyads assigned to the regular incentive condition and half to the social incentive condition. During a 5-week protocol, participants complete a 1-week baseline period, a 2-week incentive period and a 2-week post-incentive period.

Communication with participants occurred using the Way to Health (W2H) platform. Participants downloaded the FitBit and Aware apps onto their IOS or Android smart phone to track steps walked and GPS location. They completed surveys on W2H at the beginning and end of the survey. W2H sent participants text messages each morning and evening. During the baseline period participants earned \$1 for each day they synced both apps. After the baseline period all participants were assigned a daily step goal that represented a 30% increase in daily steps walked. During the incentive and post-incentive periods, the evening text message included a link to a survey where participants could self-report walking with their partner. During both of these periods, participants earned \$1 per day for syncing the apps and an additional \$1 per day for completing the evening survey. During the incentive period only, they earn \$2 per day for meeting their step goal (regular incentive) or they earn \$1 per day for meeting their step goal and an additional \$1 per day for walking at least 1 mile with their partner. At the completion of the study, participants were mailed a ClinCard debit card loaded with their payment total.

Randomization

Simple randomization to condition was accomplished via the W2H platform at the completion of the baseline period. Because W2H does not have the capacity to randomize at the level of the dyad, the research team manually adjusted conditions such that both members of a dyad were in the same study condition.

Explanation of existing data

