- Two boot-strapped mediation analyses will be conducted, one for each putative mediator.

Primary dependent variables (as pre-registered on Clinical Trials)

1. The mean daily treatment period step count (averaged across all of a participant's included treatment period days) minus the mean daily baseline period step count (averaged across all of a participant's included baseline period days).
2. The mean daily followup period step count (averaged across all of a participant's included followup period days) minus the mean daily baseline period step count (averaged across all of a participant's included baseline period days).
3. Number of days during treatment period when participant reached goal. Converted to a fraction by dividing by the number of included treatment period days.
4. Number of days during followup period when participant reached goal. Converted to a fraction by dividing by the number of included followup period days.
5. Change in score on UCLA Loneliness Scale. Score on post-test (range 0 to 60) minus score on pretest.

Secondary dependent variables (as pre-registered on Clinical Trials)

6. Number of days participant walked together with partner during treatment period, as assessed via self-report on daily survey
7. Number of days participant walked together with partner during followup period, as assessed via self-report on daily survey
8. Number of days participant walked together with partner during treatment period, as assessed via Aware data
9. Number of days participant walked together with partner during followup period, as assessed via Aware data

Main Analysis

- DV = each of the primary dependent variables shown above
- IV = condition (regular vs. social incentive)
- Data structure: 1 rows of data per participant
- Errors clustered at the dyad level
- Covariates:
 - Partners in same or different time zone (dyad level)
 - Gender, age (individual level)
 - Date of first day of baseline (individual level)
 - Lag in number of days between enrollment of first partner and enrollment of second partner (dyad level)

Exploratory HLM Analysis

- DV = daily step count
- IV
 - Fixed effect of participant
 - Dummy variable for treatment period (relative to baseline period as reference)
 - Dummy variable for followup period (relative to baseline period as reference)
 - Interaction between each dummy & condition (regular vs. social incentive)
- Data structure: 35 rows of data per participant (one for each day)

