- Clustering: days nested within participant; participant nested within dyad

Transformations

None planned.

Inference criteria

Alpha is set at .05

Data exclusion

See analysis plan

Missing data

When a participant is missing step data for an individual day, the mean daily step count for the study phase will be computed using the days with non-missing data. If a participant is missing step data for all the days in a study phase, the mean daily step count for the baseline period will be substituted (leading to a change score of 0).

If a participant is missing data from the intake survey (e.g., gender, age, or UCLA loneliness score), the study-wide mean or mode will be substituted. If a participant is missing data from the exit survey (e.g, UCLA loneliness score), the corresponding value from the intake survey will be substituted.

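### The Main Analysis set for all five primary outcomes depends on syncing after randomisation and discards observed data; name the planned ITT set as primary and replace its zero-change rule

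*SAP*

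**What the plan says.** **Timing.** "Simple randomization to condition was accomplished via the W2H platform at the completion of the baseline period" (SAP, Randomization).

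**Main set.** The inclusion rules under SAP, Main Analysis, ask for synced steps on at least 2 of 7 baseline days, and then set three further conditions:
- The first concerns the incentive phase: "Provide synced step data for at least 4 days of the 14-day treatment period".
- The second sets the same threshold for the last two weeks: "Provide synced step data for at least 4 days of the 14-day followup period".
- The third concerns the other dyad member: "Be paired with a partner who is also included in the main analyses".

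The model specification, also headed Main Analysis, applies this one set throughout: "DV = each of the primary dependent variables shown above". Those outcomes are step change in treatment (DV 1) and follow-up (DV 2), the fraction of goal days in each period (DVs 3 and 4), and change in the loneliness score (DV 5), which comes from the intake and exit surveys.

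**ITT set.** Membership is wide: "Includes all Ss who meet the inclusion criteria, even if they have a lot of missing data". The SAP then describes how this analysis relates to Main: "Similar to the main analysis described below, but it doesn't exclude Ss based on missing data". The planned data file carries a flag for each set.

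**Missing data.** For a phase with no step data, "the mean daily step count for the baseline period will be substituted (leading to a change score of 0". A missing exit survey takes the intake value, so DV 5 is also zero.

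**The concern.** Two of the Main rules rest wholly on what a person does after assignment. The third, the partner rule, imports the partner's post-assignment syncing together with the partner's pre-randomisation baseline rule. Only a participant's own baseline rule is settled entirely before assignment.

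Two things are at stake. First, observed data are thrown away, because one set built from step syncing in all phases serves outcomes that do not need all phases. Second, if passing the rules is related to the outcome differently in the two arms, the groups compared are no longer those that were randomised. The arms are paid for different things in the incentive period, so this is plausible.

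The planned ITT analysis avoids the selection. But the SAP does not say whether ITT or Main decides the conclusion, and Main is the label attached to the primary outcomes. ITT also scores wholly missing outcomes as no change. That rule does not touch people with some days in the phase. Elsewhere it shrinks true effects, and it creates a difference if both arms change and missingness differs by arm.

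**Working it through.** The documents give no power calculation, SD, effect size or sync rate, so there is no planned figure to reproduce. From the documents: 220 people enrolled, so at most 110 dyads or 55 per arm; periods of 7, 14 and 14 days; errors clustered by dyad; alpha 0.05. Everything else is assumed.

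**1. Data discarded (no assumption needed).** Take a person with 7 baseline, 14 treatment and 3 follow-up days. That is 7 + 14 + 3 = 24 usable days, complete for DVs 1 and 3. The person fails the follow-up rule and leaves all five analyses. The partner, with up to 35 usable days, leaves too.

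**2. Precision.** Let f be the share of individuals who fail. Dyads lost are 1 − (1 − f)² if partners fail independently, or f if they always fail together. With dyad ICC 0.3 (assumed) and 80% power, the detectable effect under Main is 2.80 × √[2 × 1.3 / (110 × (1 − loss))]. With no loss it is 2.80 × √(2.6/110) = 0.43 SD. If the partner rule is dropped but failers have nothing for that outcome, independent failure gives 2.80 × √[2 × (1 + 0.3(1 − f)) / (110(1 − f))].

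| f | Dyads lost, independent / together | Main, independent / together | All available data, phase wholly missing, independent |
|---|---|---|---|
| 10% | 19% / 10% | 0.48 / 0.45 SD | 0.45 SD |
| 15% | 28% / 15% | 0.51 / 0.47 SD | 0.46 SD |
| 20% | 36% / 20% | 0.54 / 0.48 SD | 0.47 SD |

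Where the failers' data for an outcome exist, as in step 1 for DVs 1 and 3, 0.43 SD is reachable. If the phase is wholly missing and partners fail together, the available data equal Main's, and nothing is gained beyond what imputation predictors add.

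**3. Bias.** Simulation of DV 2 with no true effect: 55 dyads per arm, SD of true change 1500 steps, daily SD 3500, ICC 0.3, correlation 0.7 between treatment and follow-up change, about 83–84% of individuals retained, and a dyad-clustered t test. Selection acts in the social arm only, at log-odds 0.3/0.6/1.0 per SD of true follow-up change.

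| Analysis | Failers have no follow-up days | Type I error | Failers have 2 follow-up days |
|---|---|---|---|
| Main | +98/+184/+317 | 6.1/7.8/13.4% | +92/+182/+315 |
| ITT as planned | +67/+121/+204 | 5.5/7.1/10.8% | 0/−5/+2 |
| All randomised, imputation by arm | +48/+81/+140 | 5.5/5.6/7.1% | not needed |

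With the same selection in both arms (log-odds 0.6), every analysis is within 2 steps of zero.

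**4. Zero-change rule.** With m the share missing a whole phase and μ the mean change in each arm, the expected difference is (1 − m_soc)μ_soc − (1 − m_reg)μ_reg.
- No effect, both arms +1000 steps, 10% (regular) vs 20% (social) missing: 800 − 900 = −100. With 10% vs 30%: 700 − 900 = −200. Simulation gives −94 and −197; Main, with failure unrelated to change, gives +8 and −5.
- True difference 500 (means 1000 and 500), 10% or 20% missing in both arms: the estimate is 900 − 450 = 450, or 800 − 400 = 400.

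**5. Zero included days.** DVs 3 and 4 become 0/0 in a phase with no included days. The substitution rule supplies a step mean, not a goal-day fraction.

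**The case against.** **ITT is already planned.** It has no sync or partner rule, it has its own flag, and the SAP says the plan was filed before data were downloaded from W2H. Minimum-data thresholds are a recognised choice. This stands to the extent that no new set is needed. It does not say which result decides.

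**A reader might infer that the Main comparison is biased.** The documents do not support that. Daily pay for syncing is equal in both arms, no sync rates are given, and step 3 shows no bias when selection is the same in both arms.

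**A reader might infer that the planned ITT cures only about a third of any bias.** That holds only if failers have no follow-up days. With 2 days each, the planned rule removes essentially all of it. Nor can failers be presumed to have stopped syncing. If everyone shared one daily sync rate, few would fail (0.4/2.9/12.4% of a 14-day phase at rates 0.6/0.5/0.4). If rates vary between people (beta-binomial, mean 0.7–0.9, precision 1–6, assumed), 67–99% of those failing a phase have 1–3 days. The documents do not settle which case dominates.

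**A reader might infer that the change restores 0.43 SD for every outcome.** It does not where the phase is wholly missing (step 2).

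**Imputation is not better on every measure.** With no true effect and failers without follow-up days, root mean squared error for Main/zero change/imputation (approximated by regression prediction) was 385/293/331, 426/311/341 and 490/345/358 steps. Zero change does well there partly because zero is the truth; step 4 shows what it does otherwise.

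**The common +1000 steps is assumed.** A goal 30% above baseline is not an outcome, and goal payments end before follow-up. Step 4 scales in proportion to whatever the common change is.

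**Conclusion.** The concern holds. From the text alone, a set that depends on post-randomisation syncing and on the partner's status is applied to all five primary outcomes. It removes observed data from DVs 1, 3 and 5, and the SAP does not say whether Main or ITT decides. Confidence in this, and in the choice of primary set, is high.

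The size is conditional. The +98 to +317 steps under Main require selection that differs by arm. The planned ITT's share of that bias ranges from about two thirds to none, according to how many days failers provide. The precision gain runs from a fall in the detectable effect from 0.54 to 0.43 SD (20% failing independently, data present) down to nothing (partners failing together, phase wholly missing). Confidence in the magnitudes and in imputation as the remedy is moderate, since only DV 2 was simulated, with three imputation predictors.

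This should be fixed, but the documents do not show that the trial's comparison is invalid.

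**What to change.** 1. State that the planned ITT set, without sync thresholds or the partner rule, is primary for the five primary DVs. Keep dyad-clustered errors, which allow a dyad with one contributing member. Keep the threshold set as a sensitivity analysis, and report exclusions by arm and by rule.
2. Use the observed phase mean whenever a phase has at least one included day. For a wholly missing phase or exit survey, do not use zero change as the primary rule. Use multiple imputation with arm, the baseline or intake value, the other phase and the planned covariates. For DVs 1–2 the daily-step model in the Exploratory HLM Analysis, fitted to all randomised participants, is an alternative. Report zero change, and imputed values shifted by arm, as sensitivity analyses. Imputation also covers the 0/0 fraction in DVs 3–4.
3. Reconcile the exclusion of people who ask to unenrol, which has no time limit in the Inclusion Criteria of either document, with the SAP flow diagram, which places it before randomisation.

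**Cost.** The ITT set and its flag exist, so the work is a statement of the primary set, an imputation step, one clarified criterion, and a dated amendment if data have been opened. Some phase means will rest on 1–3 days. Imputation assumes data are missing at random; when failure depends on unseen follow-up change it removed only about half of the bias (51–56% in step 3), and its mean squared error can exceed that of zero change when there is no true effect. The daily model weights people by days, so with failers giving 2 days it kept +28/+54/+100 steps of bias where unweighted phase means kept about none.
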